3.3 Subject Enrollment and Randomisation

Procedures for withdrawal of incorrectly enrolled or randomised subjects are described in section 3.4.

Investigator(s) should keep a record of subjects considered for and included in the study on the subject screening log.

The Investigator will:

1. Obtain signed informed consent from the potential subject before any study specific procedures are performed.
2. Assign each potential subject a unique enrolment number, beginning with 'E# via interactive web/voice response system (IWRS/IVRS)
3. Determine subject eligibility.
4. Assign eligible subject unique randomisation code via IWRS/IVRS

Subjects will be allocated to the four treatment arms in a 1:1:1:1 ratio. The randomisation numbers will be grouped in blocks. The study will recruit approximately 2168 subjects, randomised 1:1:1:1 to the treatment arms, stratified by country and blood eosinophil count ($\geq 300/\mu\text{L}$ and $< 300/\mu\text{L}$ strata). Subject recruitment will be capped at the study level for the cohorts with baseline eosinophil counts $< 220/\mu\text{L}$, $220\text{-}299/\mu\text{L}$, and $\geq 300/\mu\text{L}$ in order to keep predefined cohort sample size and approximately 2:1 ratio of subjects above and below the boundary of $220/\mu\text{L}$. Details of the estimated numbers of recruited subjects/arm in each cohort ($< 220/\mu\text{L}$, $220\text{-}299/\mu\text{L}$, $\geq 300/\mu\text{L}$) are described in the SAP. It is expected that the $< 220/\mu\text{L}$ cohort will fill first based on prevalence. Instructions for screen failing these subjects from the study after a stratum is closed are noted in the protocol (Section 3.7.2).

Specific information concerning the use of the IWRS/IVRS will be provided in a separate manual. If a subject withdraws from participation in the study, then his/her enrolment/randomisation code cannot be reused. Withdrawn subjects will not be replaced.

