8.2 Sample size estimate

The study will recruit subjects with blood eosinophil counts $<220/\mu\text{L}$, $220\text{-}299/\mu\text{L}$, and $\geq 300/\mu\text{L}$. The approximately 2:1 ratio between $\geq 220/\mu\text{L}$ and $<220/\mu\text{L}$ allows analysis of the primary population for subjects most likely to respond to benralizumab (i.e. $\geq 220/\mu\text{L}$), while still including subjects below this threshold in order to help understand efficacy and safety in this group. The study is powered for the exacerbation rate comparisons of the subjects with blood eosinophils $\geq 220/\mu\text{L}$ (primary efficacy analysis).

For the primary endpoint annual COPD exacerbation rate, 348 subjects with baseline blood eosinophil counts $\geq 220/\mu\text{L}$ per treatment arm (1392 total) will need to be randomised to achieve 90% power of detecting a 30% reduction in both the 30mg and 100mg benralizumab dose groups versus placebo based on a Hochberg Procedure (Hochberg 1988). This calculation has assumed two-sided 4% alpha level tests, an annual placebo rate of 0.93 events/subject (1.0 events/subject/56 weeks), a negative binomial shape parameter of 0.4, and a dropout rate of 10%. The sample size calculation is based on simulations and has accounted for the power loss from a proposed futility analysis (Section 8.5.6).

As stated previously an approximately 2:1 ratio will be used for subjects with blood eosinophil counts $\geq 220/\mu\text{L}$ and $<220/\mu\text{L}$. Therefore this study will randomise 174 subjects/arm (696 total) with baseline blood eosinophil counts $<220/\mu\text{L}$. An additional 20 subjects/arm will also be recruited to the 220-299/ μL cohort to better characterize patients within this cohort. This addition results in 368 subjects/arm in the $\geq 220/\mu\text{L}$ cohort (1472 total). A total of 2168 subjects are expected to be randomised in this study. Details of the estimated numbers of recruited subjects/arm in each cohort ($<220/\mu\text{L}$, $220\text{-}299/\mu\text{L}$, $\geq 300/\mu\text{L}$) are described in the SAP.

The sample size necessary to achieve a stated power (90% in our case) in this study is calculated based on the estimate of overall exacerbation rate and shape parameter from the negative binomial model (Section 8.5.1). In order to better estimate the overall exacerbation

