rate and shape parameter, we plan to conduct a single blinded sample size re-estimation in both studies D3251C0003 and D3251C0004. Blinded estimates of the overall exacerbation rate as well as the shape parameter from data pooled across placebo and all benralizumab doses (for patients with eosinophil counts $\geq 220/\mu\text{L}$) will be used in the sample size re-estimation and strictly no treatment information will be used in the review. The pooled study summaries will not contain any information that would potentially reveal the treatment assignments (e.g., post-randomization eosinophil levels). The review will be conducted before the last patient with eosinophil counts $\geq 220/\mu\text{L}$ is randomized and after the futility analysis (Section 8.5.6). The exacerbation rate and shape parameter will be estimated using the maximum likelihood approach as proposed by [Friede and Schmidli 2010](#). This review may result in an adjustment of sample size. Since this review will be performed in a blinded fashion, no adjustment for the type I error is needed. The blinded data review will be performed by AstraZeneca internal personnel or its designees and the full details of the review will be specified in a blinded data review plan.

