8.4.3 Calculation or derivation of patient reported outcome variables

SGRQ

Potential health status treatment benefits of benralizumab will be evaluated by comparing the change from baseline at Week 56 in SGRQ Total scores. For the responder analysis of SGRQ

a responder will be defined as an individual with a ≥ 4 -point decrease (improvement) in SGRQ total score at Week 56.

E-RS

Respiratory symptoms will be evaluated using the E-RS. Individual daily E-RS total and subscale scores will be calculated and summarized as a biweekly (14 day) mean. Data collected in the two-week period prior to randomisation will be used to calculate the individual E-RS total and subscale baseline means.

EXACT-PRO

The number, average duration, and severity of EXACT-PRO defined events will be evaluated. EXACT-PRO daily total scores as well as domain scores will be calculated according to the developer approved scoring algorithm. The total score will be used to identify event onset and recovery as well as the magnitude (severity) of the event. The baseline total score will be the mean within subject score over the 7 days prior to randomisation. A minimum of 4 days of data is required for calculating the baseline total score. To allow for improvement or deterioration in disease state over the course of the trial, the baseline total score should be reset every 4 weeks in the absence of an EXACT-PRO defined event. Event frequency is calculated by comparing the baseline with daily total scores. Calculating event duration requires identification of the following five parameters: 1) onset; 2) three-day rolling average; 3) maximum observed value; 4) threshold for improvement; and 5) recovery. The severity of an event is indicated by the worst (highest) EXACT-PRO total score during an event. Complete details concerning variable calculation are provided in the scoring manual and will be provided in the study Statistical analysis plan (SAP).

BDI/TDI

The instrument consists of three components: functional impairment, magnitude of task, and magnitude of effort. For the BDI, each of these three components are rated in five grades from 0 (severe) to 4 (unimpaired), and are summed to form a baseline total score from 0 to 12. The BDI will be captured at baseline only. For the TDI, changes in dyspnea are rated for each component by seven grades from -3 (major deterioration) to +3 (major improvement), and are added to form a total TDI score from -9 to +9.

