8.5 Methods for statistical analyses

The primary analysis of the primary and key secondary endpoints will include all data captured during the 56-week treatment period, regardless of whether study treatment was prematurely discontinued, or delayed, and/or irrespective of protocol adherence.

Demography and baseline characteristics will be summarized by treatment group for the full analysis set. In the event that there are major differences between the full analysis set and safety analysis set, these summaries will also be repeated for the safety analysis set.

Testing strategy to account for multiplicity considerations

To account for multiplicity to test the primary (exacerbation) and two key secondary endpoints (FEV₁ and SGRQ) for each of the 30mg and 100mg dose groups (for subjects with baseline blood eosinophils $\geq 220/\mu\text{L}$) a testing strategy will be followed to control the overall type I error rate at level 0.05. The testing strategy will be according to the following gate keeping procedure:

Step 1: Perform the two tests of annual COPD exacerbation rate (one test for each dose vs. placebo) at the family wise error rate (FWER) of 0.04 using a Hochberg Procedure ([Hochberg](#))

[figure not shown]
1988). If both p-values are less than 0.04, then proceed to Step 2; else if the smaller p-value is less than 0.02 then proceed to Step 2a; otherwise no null hypothesis is rejected

Step 2: Test the two key secondary endpoints for both doses as one family at the FWER of 0.05 using a Holm Procedure (Holm 1979).

Step 2a: Test the two secondary endpoints for the smaller-p-value dose at the FWER of 0.01 using a Holm Procedure.

The gatekeeping procedure is also shown in the diagram below:

Figure 4 Gatekeeping Procedure

Since the correlation of the two test statistics for COPD exacerbation rate in the Step 1 is positive, the FWER of the Hochberg Procedure is strongly controlled at 0.04. The overall FWER of the gatekeeping procedure is strongly controlled at 0.05.

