8.5.2 Secondary analysis methods

8.5.2.1 Analysis methods for secondary efficacy variables

Key secondary efficacy endpoints in this study are:

- Change from baseline in pre-dose/pre-bronchodilator FEV₁ at Week 56
- Change from baseline in SGRQ total score at Week 56

Other secondary efficacy endpoints include

- Proportion of subjects with ≥ 1 COPD exacerbation

- Time to the first COPD exacerbation
- Proportion of subjects with ≥ 4 -point decrease (improvement) in SGRQ total score at Week 56
- Annual rate of COPD exacerbations that are associated with an emergency room visit or a hospitalization
- Annual rate of hospitalizations, annual rate of hospitalizations and emergency room visits combined, annual rate of unscheduled outpatient visits including unscheduled visits to study centres and all unscheduled healthcare encounters due to COPD
- Rescue medication use (average puffs/day)
- Number of nights with awakening due to COPD and requiring rescue medication
- Change from baseline in E-RS total score and domain scores at Week 56
- Area under the curve (AUC) of E-RS total score
- BDI/TDI
- CAT
- EXACT-PRO

All the secondary efficacy endpoints will be analyzed in subjects with baseline blood eosinophil counts $\geq 220/\mu\text{L}$. In addition, the two key secondary endpoints will also be summarized in subjects with baseline blood eosinophil counts $< 220/\mu\text{L}$, $< 150/\mu\text{L}$, $150-219/\mu\text{L}$, $220-299/\mu\text{L}$, $300-449/\mu\text{L}$, and $\geq 450/\mu\text{L}$ separately for descriptive purpose only.

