Change from baseline in pre-dose/pre-bronchodilator FEV_1 at Week 56 will be compared between each of the three benralizumab dose groups and placebo using a repeated measures analysis on subjects with a baseline pre-dose/pre-bronchodilator FEV_1 and at least one post-randomisation pre-dose/pre-bronchodilator FEV_1 in the full analysis set. The dependent variable will be the change from baseline in pre-bronchodilator FEV_1 at post-baseline protocol-specified visits (up to the EOT visit). Treatment group will be fitted as the explanatory variable, and eosinophil cohort ($220-299/\mu\text{L}$ or $\geq 300/\mu\text{L}$), country, background therapy (ICS/LABA, LABA/LAMA, or ICS/LABA/LAMA), visit, the interaction between visit and treatment and baseline pre-bronchodilator FEV_1 will be fitted as covariates. Visit will be fitted as a categorical variable, and the variance-covariance matrix will be assumed to be unstructured. If the procedure does not converge then a compound symmetric variance-covariance matrix will be used instead. The model is:

*Change in FEV₁ = Treatment group + eosinophil cohort (220-299/ μ L or \geq 300/ μ L) + baseline FEV₁ + country + background therapy (ICS/LABA, LABA/LAMA, or ICS/LABA/LAMA) + visit + treatment*visit*

Change from baseline in SGRQ total score and three domain scores (symptoms, activity, and impacts) at Week 56 will be analyzed separately using a similar model as the above model for change from baseline in pre-dose/pre-bronchodilator FEV₁.

Proportion of subjects with \geq 4-point decrease (improvement) in SGRQ total score at Week 56 in each of the three benralizumab dose groups will be compared with the proportion in the placebo group using a Cochran–Mantel–Haenszel test controlling for eosinophil cohort (220-299/ μ L or \geq 300/ μ L), country, and background therapy (ICS/LABA, LABA/LAMA, or ICS/LABA/LAMA). Cumulative distribution function of absolute changes in SGRQ total score at week 56 will be plotted in a figure.

The proportion of subjects with \geq 1 COPD exacerbation during the 56 weeks of treatment will be addressed as a supportive variable to the primary objective. The proportion in each of the three benralizumab dose groups will be compared with the proportion in the placebo group using a logistic regression model with eosinophil cohort (220-299/ μ L or \geq 300/ μ L), country, background therapy (ICS/LABA, LABA/LAMA, or ICS/LABA/LAMA), and number of exacerbations in the year before the study as covariates.

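### The SGRQ responder test is a valid but sparse CMH: up to 144 strata for 736 patients, costing roughly 8–18% of the information against 1–2% for main-effects adjustment

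*Protocol*

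**What the plan says.** Protocol 8.5.2.1 analyses the SGRQ responder proportion at Week 56 dose by dose: it "will be compared with the proportion in the placebo group using a Cochran–Mantel–Haenszel test controlling for eosinophil cohort" (220–299 or ≥300/µL), country and background therapy (three classes). All secondary efficacy analyses are in patients with ≥220/µL. The synopsis plans 24 countries, and section 8.2 gives the cohort size: "This addition results in 368 subjects/arm in the" ≥220/µL cohort. That number could move, since section 8.2 also says of the blinded review: "This review may result in an adjustment of sample size".

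Randomisation (section 3.3) is 1:1:1:1, stratified by country and by ≥300 versus <300/µL: "The randomisation numbers will be grouped in blocks". Background therapy is not a stratification factor.

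The endpoint stands in the list that opens "Other secondary efficacy endpoints include". The testing strategy in section 8.5 is limited in scope: "To account for multiplicity to test the primary (exacerbation) and two key secondary endpoints". For the other binary endpoint, the proportion with at least one exacerbation, section 8.5.2.1 compares each dose with the "placebo group using a logistic regression model with eosinophil cohort", country, therapy and prior exacerbation count as covariates.

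**The concern.** A CMH test on three factors cross-classifies them. With 24 countries the cells become very small. The country and eosinophil blocks keep the arms close to balanced, but splitting them by an unstratified factor undoes much of that balance. The 220–299/µL cohort is not a block of its own either: it shares the <300/µL blocks with patients below 220/µL. A stratum with patients from one arm only adds nothing to the statistic, and an unbalanced stratum adds less than its size suggests. A model with the same factors as main effects uses far fewer parameters and pays a much smaller price.

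What is at stake is power on one other secondary endpoint. Bias, type I error, the gatekeeping and the sample size are not in question. Two binary secondary endpoints in one section are handled by different methods with no reason given, and the less efficient method falls on the responder analysis.

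**Working it through.** **Plan's own figures.** 348 + 20 = 368 per arm; 4 × 368 = 1472; 1472 + 696 = 2168, as stated. A negative binomial calculation for the primary endpoint (30% reduction in both doses, shape 0.4, two-sided 4%) gives 88.8–90.1% power after the futility rule, in line with the stated 90%. The protocol gives no power or stratum count for the responder test.

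**Stratum count.** 2 cohorts × 24 countries × 3 therapies = 144. Each comparison has 2 × 368 = 736 patients, and 736/144 = 5.1 per stratum over both arms.

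**Formulas.** Up to a common factor, the CMH information in stratum k is n1k·n0k/nk. A stratum of 5 split 3:2 gives 6/5 = 1.2; split 4:1 gives 4/5 = 0.8; split 5:0 gives 0. Relative information is Σ(n1k·n0k/nk)/(N/4). For main effects it is the residual sum of squares of the arm indicator, after regression on cohort + country + therapy, divided by N/4.

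**Simulation.** All 2168 patients were allocated to four arms in permuted blocks of 4 or 8 within country × (≥300 / <300/µL), with the 696 patients below 220/µL in the <300 blocks. Patients at ≥220/µL in placebo and one dose were kept. Inputs the protocol does not give were assumed:
- country sizes equal, or log-normal with SD 0.8 or 1.2
- therapy mix 35/15/50, 20/10/70 or 33/33/33
- share at ≥300/µL 60% or 75%
- Week 56 data complete, or 10% missing (about 662 patients)

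This makes 3 × 3 × 2 × 2 × 2 = 72 scenarios including block size, with 150 draws each. Further runs put 80–87% of patients on one therapy, changed the cohort total, or pooled countries.

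| Analysis | Loss, complete data | Loss, 10% missing |
|---|---|---|
| CMH as written | 10.7–15.6% | 11.9–18.1% |
| CMH, one therapy covering 80–87% | 7.9–11.7% | 8.9–13.0% |
| CMH, uneven countries, those under 15 patients pooled | 7.8–11.5% | 8.3–12.6% |
| CMH, 6 regions (36 strata) | 3.7–4.0% | 4.1–4.5% |
| CMH, 4 regions (24 strata) | 2.4–2.7% | 2.8–3.1% |
| Main effects, same three factors | 0.9–1.5% | 1.3–1.9% |

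In patients, the first row with complete data is 0.107 × 736 ≈ 79 to 0.156 × 736 ≈ 115, against 0.009 × 736 ≈ 7 to 0.015 × 736 ≈ 11 for main effects. About 6–10% of patients fall in one-arm strata (3–6% with uneven countries and small ones pooled).

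A separate run with other country patterns gave 9.5–15.6% with complete data, 10.6–17.8% with 10% missing and 7.6–8.4% under very skewed mixes, against 0.8–2.0% for main effects. If the blinded review moved the ≥220/µL total to 1800–2000, the CMH loss would be 8.5–12.7% with complete data; at 1200 it would be 12.5–18.6%.

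**Power.** As a direct check, take 40.0% versus 51.1% responders (odds ratio 1.57) with 368 per arm. Power is 85.8% with full information, 85.2% after a 1.5% loss, 82.8% after 8%, 80.4% after 13.5% and 78.3% after 18%.

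Simulated trials (2,000 per setting; 40% placebo response assumed; 10% missing; small countries pooled in both methods) gave:
- odds ratio 1.5: CMH 64–69%, logistic 71–73%
- odds ratio 1.6: CMH 77–80%, logistic 84–85%

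The gap is 4–5 points with uneven countries and 7–8.5 points with equal ones.

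**Type I error** (6,000 trials per setting). CMH 4.6–5.5%, logistic 5.2–5.6%. The small logistic excess explains about 1 point of its power.

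**The case against.** CMH and main-effects logistic regression are both standard and valid for a binary endpoint, so the protocol states nothing false here. The alpha-controlled SGRQ analysis is the "change from baseline at Week 56 in SGRQ Total scores", which already uses a main-effects repeated-measures model with baseline; the responder proportion is its dichotomised companion. Every loss figure rests on country, therapy and cohort mixes that the protocol does not give. The top of the range, 18%, needs missing Week 56 data: if a missing score counted as non-response, all 736 patients would stay in and the maximum would be 15.6%. The SAP, which is not shown, may pool small countries. With uneven countries, probably the more realistic case, the power gap is 4–5 points, about 1 of which is the logistic size excess.

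All of this stands as a limit on importance. It does not remove the point. The protocol fixes both the test and its factors, and pooling small countries still leaves a loss of about 8–13% when countries are uneven and changes nothing when they are equal. In every scenario examined, CMH as written lost several times as much information as main effects.

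**Conclusion.** The point holds, as an optional improvement. As written, the test loses about 8–16% of the information with complete data and about 9–18% with 10% missing, against 1–2% for main effects. The 144 strata and 736 patients follow from the protocol, although 144 is a maximum and 736 may change. The percentages depend on the assumed mixes and on stratified blocks of 4 or 8; with very uneven countries and 87% of patients on one therapy the loss falls to about 7%. Confidence in the direction is high and in the exact size moderate. The consequence is a modest, avoidable loss of power on an endpoint outside the multiplicity procedure.

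**What to change.** In section 8.5.2.1, analyse the SGRQ responder proportion by logistic regression with treatment, eosinophil cohort, country and background therapy as main effects, the form already used there for the proportion with an exacerbation. Add baseline SGRQ total score, which Table 3 schedules at Visit 4. Under an assumed log odds ratio of 0.5 per SD it adds 1.4–2.8 points of power, and nothing if that coefficient is zero. Pre-specify a rule for pooling small countries, both for efficiency and to avoid sparse country terms.

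If CMH is preferred, keep cohort and therapy and replace country with a few pre-specified regions. Four regions cut the loss to 2.4–3.1% and leave power 1.3–3.4 points below logistic. This is the second choice: it coarsens a randomisation factor, and the regions simulated were arbitrary groupings.

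The cost is wording. No patient, visit or data item is added. The logistic model reports a conditional odds ratio, and either option needs a pooling rule fixed in advance.

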5.1.4 Healthcare Resource Utilization

Broad-based COPD related health care utilization event information will be collected by the Investigator/authorized delegate in accordance with the schedule provided in [Table 3](#) and recorded in the appropriate eCRF module.

At Visit 4 (week 0) COPD related Healthcare Resource Utilization information will be collected with a one year recall period. All the subsequent visits will collect COPD related Healthcare Resource Utilization information with a recall period of ‘since last scheduled visit’.

Note: cases of hospitalization also must be reported as an SAE (see section [7.1.2](#) and [7.1.9](#)).

5.1.5 Clinician Global Impression of Change (CGIC) and Patient Global Impression of Change (PGIC)

The Clinician Global Impression of Change (CGIC) and Patient Global Impression of Change (PGIC) instruments are used to evaluate overall response to treatment (change from baseline). The assessments are independent of each other. The subject completes the assessment without reference to the clinician’s rating and the clinician completes the assessment without reference to the subject’s rating. Both assessments use a 7-point rating scale: 1 = Very Much Improved; 2 = Much Improved; 3 = Minimally Improved; 4 = No Change; 5 = Minimally Worse; 6 = Much Worse; and 7 = Very Much Worse.

The investigator (clinician) and the subject will be asked to rate the degree to which overall COPD status may have changed when compared to baseline (i.e. randomization visit/initiation of study drug). The CGIC and PGIC will be completed at the site visits as indicated in [Table 3](#). It is recommended that the same clinician completes the CGIC for an individual subject.

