8.4.1.6 Annual rate of healthcare encounters due to COPD

The annual rate of hospitalizations due to COPD, the annual rate of hospitalizations and emergency room visits combined due to COPD, the annual rate of unscheduled outpatient visits including unscheduled visits to study centres due to COPD and all unscheduled healthcare encounters combined due to COPD (hospitalizations, emergency room visits, unscheduled outpatient visits including unscheduled visits to study centres) will be secondary variables.

In the statistical analysis, the number of hospitalizations due to COPD, the number of emergency room visits and hospitalizations combined due to COPD, the number of unscheduled outpatient visits due to COPD and the number of all unscheduled healthcare encounters due to COPD experienced by a subject during the 56-week double-blind treatment period will be used as response variables in four different statistical models with the logarithm of the subject's corresponding follow-up time used as an offset in the analysis to adjust for subjects having different exposure times similar to COPD exacerbations as described in section 8.4.1.5. If multiple healthcare encounters are associated with one COPD exacerbation all the encounters will be counted for this endpoint.

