8.5.1 Primary analysis method(s)

The primary efficacy variable is the annual COPD exacerbation rate and the primary analysis is to compare the annual COPD exacerbation rate of each benralizumab dose group with placebo in subjects with baseline blood eosinophil counts $\geq 220/\mu\text{L}$.

For each of the three benralizumab dose groups, the null hypothesis is that the exacerbation rate on benralizumab is equal to the exacerbation rate on placebo. The alternative hypothesis is that the exacerbation rate on benralizumab is not equal to the exacerbation rate on placebo, i.e.:

H₀: Rate ratio (benralizumab vs. Placebo) = 1

H_a: Rate ratio (benralizumab vs. Placebo) \neq 1

Exacerbation rate in each of the three benralizumab dose groups will be compared to exacerbation rate in the placebo group using a negative binomial model. The response variable in the model will be the number of COPD exacerbations over the 56-week treatment period. The model will include covariates of treatment group, eosinophil cohort (220-299/ μL or $\geq 300/\mu\text{L}$), country, background therapy (ICS/LABA, LABA/LAMA, or ICS/LABA/LAMA), and the number of exacerbations in the year before the study. The logarithm of the follow-up time will be used as an offset variable in the model.

The estimated treatment effect (i.e., the rate ratio of benralizumab versus placebo), corresponding 95% confidence interval (CI), and two-sided p-value for the rate ratio will be presented. In addition, the exacerbation rate and the corresponding 95% CI within each treatment group will be presented.

In addition, the exacerbation rate will also be summarized in subjects with baseline blood eosinophil counts $< 220/\mu\text{L}$, $< 150/\mu\text{L}$, 150-219/ μL , 220-299/ μL , 300-449/ μL , and $\geq 450/\mu\text{L}$ separately for descriptive purpose only.

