Time to first COPD exacerbation will be analyzed as another supportive efficacy variable to the primary objective to explore the extent to which treatment with benralizumab delays the time to first exacerbation compared with placebo. A Cox proportional hazard model will be fitted to data with the covariates of treatment, eosinophil cohort (220-299/ μ L or \geq 300/ μ L), country, background therapy (ICS/LABA, LABA/LAMA, or ICS/LABA/LAMA), and number of exacerbations in the year before the study.

Annual rate of COPD exacerbations that are associated with an emergency room visit or a hospitalization will be analyzed using a similar Negative binomial model as outlined for the primary efficacy variable in section 8.5.1.

Annual rates of hospitalizations, hospitalizations and emergency room visits combined, unscheduled outpatient visits including unscheduled visits to study centres as well as all unscheduled healthcare encounters due to COPD (hospitalizations, emergency room visits, and unscheduled outpatient visits including unscheduled visits to study centres) will be analyzed using Negative Binomial Models as outlined for the primary efficacy variable in section 8.5.1.

The number of nights with awakening due to COPD and requiring rescue medication will be analyzed as the response variable by fitting a repeated measures model to data. Treatment group will be fitted as the explanatory variable, and eosinophil cohort (220-299/ μ L or \geq 300/ μ L), country, baseline value and background therapy (ICS/LABA, LABA/LAMA, or ICS/LABA/LAMA) will be fitted as covariates. Rescue medication use (average puffs/day) will be analyzed using a similar model.

Change from baseline in E-RS total score and domain scores at Week 56 will be analyzed separately using a similar model as the model for change from baseline in pre-dose/pre-bronchodilator FEV₁. AUC of E-RS total score will be analyzed by fitting an ANCOVA model with treatment, eosinophil cohort (220-299/ μ L or \geq 300/ μ L), country, baseline value, and background therapy (ICS/LABA, LABA/LAMA, or ICS/LABA/LAMA) as covariates.

The BDI/TDI, EXACT-PRO, and CAT will be summarized by treatment and visit.

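### The four healthcare-use models do not adjust for the prior-year COPD healthcare use recorded at Visit 4: valid comparisons, but some precision is lost, mainly for frequent encounters

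*Protocol*

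**What the plan says.** Protocol section 8.4.1.6 defines four outcomes: COPD hospitalisations, hospitalisations and emergency room visits combined, unscheduled outpatient visits (study-centre visits included), and all unscheduled encounters. These "will be used as response variables in four different statistical models", with log follow-up time as offset. If one exacerbation leads to several encounters, all of them count.

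Section 8.5.2.1 states that these rates "will be analyzed using Negative Binomial Models as outlined for the primary efficacy variable in section 8.5.1". Section 8.5.1 lists the covariates of that model: treatment, eosinophil cohort, country, background therapy "and the number of exacerbations in the year before the study". Each of the three doses is compared with placebo, so four models give 4 × 3 = 12 comparisons.

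Section 5.1.4 says: "At Visit 4 (week 0) COPD related Healthcare Resource Utilization information will be collected with a one year recall period". Later visits collect the same information since the previous scheduled visit. The protocol names no analysis that uses the Visit 4 record.

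Elsewhere section 8.5.2.1 adjusts for the endpoint's own baseline. The FEV1 model includes baseline FEV1. Nights with awakening are adjusted for "country, baseline value and background therapy" as well as eosinophil cohort, rescue use has a similar model, and the E-RS AUC model also has a baseline value.

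**The concern.** A pre-treatment measurement of an outcome is usually among its strongest predictors. Here one is collected before the first dose, and the covariate list, fixed by cross-reference, passes over it.

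The prior exacerbation count is an imperfect substitute, for two reasons in the protocol itself.

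- Inclusion criterion 4 admits two or more moderate exacerbations or one or more severe ones. A subject who qualifies with exactly one must have been hospitalised, while a subject with two or three may never have been. At its low end the total count therefore orders subjects poorly for hospitalisation history.
- Section 8.4.1.6 counts every encounter within an exacerbation. The outcome therefore also reflects how many encounters a subject generates per exacerbation, which an exacerbation count cannot carry.

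What is at stake is the width of the confidence intervals on the healthcare-use objective.

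**Working it through.** **1. The plan's own figure.** The protocol gives design figures only for the primary endpoint (section 8.2): "90% power of detecting a 30% reduction in both the 30mg and 100mg benralizumab dose groups versus placebo" with 348 subjects per arm, two-sided alpha 0.04, "an annual placebo rate of 0.93 events/subject (1.0 events/subject/56 weeks"), shape parameter 0.4 and 10% dropout.

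- Rate check: 1.0 × 365.25/392 = 0.93 per year. Consistent.
- Variance of the log rate ratio: (1/μ0 + 1/μ1 + 2k)/n = (1/1.0 + 1/0.7 + 2 × 0.4)/348 = 3.229/348 = 0.00928, so SE = 0.0963.
- Power for both doses, simulated with a shared placebo arm: 91.1% with no losses; 89.8% with dropout taken as a 5% mean loss of exposure; 88.6% with the futility look added.

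The stated 90% is reproduced to within 2 points, so the same variance formula is a fair tool for the healthcare-use rates.

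**2. What a baseline covariate can gain.** It can remove only part of the dispersion k, not the Poisson part 1/μ. If a share s of k is removed beyond what prior exacerbations already explain, the SE is multiplied by

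√[(1/μ + 1/(0.7μ) + 2k(1 − s)) / (1/μ + 1/(0.7μ) + 2k)].

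Example with μ = 0.2, k = 1.0, s = 0.3: √(13.543/14.143) = 0.979, a fall of 2.1%. With μ = 1.0 and the same k and s: √(3.829/4.429) = 0.930, a fall of 7.0%.

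The values of μ, k and s are assumptions. The only dispersion in the protocol is 0.4, for the primary endpoint.

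| Assumed placebo rate per 56 weeks | Smallest fall in SE (k = 0.4, s = 0.1) | Largest fall in SE (k = 2.0, s = 0.5) |
|---|---|---|
| 0.2 | 0.3% | 6.4% |
| 0.4 | 0.6% | 10.5% |
| 1.0 | 1.2% | 17.0% |
| 2.0 | 2.0% | 21.5% |

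**3. Simulation with the exacerbation count already in the model.** Negative binomial fits used 368 subjects per arm (348 + 20, section 8.2) and 60 to 80 replicates per scenario. Each scenario compared the prior exacerbation count alone with the same count plus log(1 + prior use). Assumed inputs: frailty SD 0.8 to 1.2, correlation 0.3 to 0.7, year-to-year persistence 0.5 to 0.8. The gain in effective sample size is (SE without / SE with)² − 1. Percentages come from unrounded SEs.

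| Outcome (assumed rate) | End of range | SE without → with | Change in SE | Gain in effective N |
|---|---|---|---|---|
| Hospitalisations (0.2-0.3) | low | 0.1958 → 0.1956 | −0.1% | 0.1% |
| | high | 0.2151 → 0.2099 | −2.4% | 5.0% |
| Hospitalisations + ER (0.4) | low | 0.1428 → 0.1407 | −1.4% | 3.0% |
| | high | 0.1672 → 0.1593 | −4.8% | 10.2% |
| All encounters (1.5) | low | 0.0911 → 0.0894 | −1.9% | 3.8% |
| | high | 0.1172 → 0.1022 | −12.8% | 31.4% |

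The high ends all need wide, persistent differences between subjects (frailty SD 1.2, persistence 0.8). Unscheduled outpatient visits were not simulated separately; a rate near 1 to 2 falls in the lower rows of the first table.

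**The case against.** The strongest reply is that nothing here is wrong. The model is pre-specified and already carries a disease-history term, and country absorbs between-country differences in health systems. These are other secondary endpoints outside the gatekeeping procedure, and the study is not powered on them. The statistical analysis plan is not at hand and could add the covariate. All of this stands as a limit on severity. It does not remove the point, because sections 8.5.1 and 8.5.2.1 together do state a covariate list and prior use is not in it.

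Three stronger readings are tempting, and the protocol does not support them.

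- A reader might infer bias or an invalid test. In a randomised comparison, leaving out a prognostic covariate costs efficiency and does not invalidate the estimate.
- A reader might infer that worthwhile precision is lost on all four outcomes. For rare hospitalisations the Poisson term dominates and the gain is close to nil.
- A reader might take the Visit 4 record as an exact baseline for each outcome. Two outcomes include unscheduled study-centre visits, which the trial itself partly generates: diary alerts prompt contact with the centre (section 5.1.3.7), and worsening is to be evaluated there when feasible (section 4.2.1). The prior year has no like-for-like value. The match is therefore weakest for the frequent outcomes, where the larger gains were calculated, and the upper end of that range should be read with caution.

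One further caveat stands: section 5.1.4 describes the Visit 4 information broadly and does not say that counts by encounter type are recorded.

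**Conclusion.** The point holds as a minor, optional improvement. The four models omit a pre-treatment value that the trial already collects, unlike the protocol's handling of FEV1, nights with awakening, rescue use and E-RS AUC. All 12 comparisons remain valid. The likely loss in effective sample size is about 0-5% for hospitalisations, 3-10% for hospitalisations plus emergency room visits, and 4-31% for all encounters. These ranges rest wholly on assumed rates, dispersions, correlations and persistence, none of which the protocol supplies. They should be read as showing where the gain lies (frequent encounters, stable individual habits), not as a forecast.

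**What to change.** In section 8.5.2.1, before unblinding, add one covariate to each healthcare-use model and keep the prior exacerbation count:

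- The Visit 4 prior-year count of the corresponding encounter type, entered for example as log(1 + count), or as a collapsed category if the counts are sparse.
- For the two outcomes that include study-centre unscheduled visits, prior-year unscheduled outpatient visits or all prior-year encounters respectively, as the nearest available baseline.
- In the model for exacerbations with an emergency room visit or hospitalisation, which section 8.5.2.1 describes only as similar to the primary model, the prior-year count of hospitalisations and emergency room visits from the same Visit 4 record, alongside the total exacerbation count.

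Check first that the eCRF module separates encounter types, and state in advance how missing recalled values are handled.

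The cost is a wording change and one extra term per model, with a few missing values. If the module separates encounter types, no new visit or data collection is needed. The choice has to be fixed before unblinding, because adding the covariate afterwards would be post hoc.
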